## 6.3. Measures to Minimize Bias: Randomization and Blinding

### Randomization and stratification

All participants will be centrally randomized and assigned to LY3209590 or insulin glargine using an IWRS. Before the study is initiated, the login information and directions for the IWRS will be provided to each site.

Participants will be randomly assigned in a 1:1 ratio to LY3209590: insulin glargine.

Participants will be stratified based on

- country
- HbA1c stratum (<8% and  $\geq$ 8%) at Visit 1
- Routine use of personal CGM or FGM at randomization (yes/no)

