## 1.1. Objectives, Endpoints, and Estimands

Objectives	Endpoints
Primary	
Demonstrate noninferiority of LY3209590 compared to insulin glargine on glycemic control.	Change in HbA1c from baseline at Week 26
Key Secondary (Multiplicity Adjusted)	
Demonstrate LY3209590 is superior to insulin glargine in the selected parameters of glycemic control.	
 
Change in HbA1c from baseline at Week 26
 
The percentage of participants achieving HbA1c <7% at Week 26 without nocturnal hypoglycemia (<54 mg/dL [3.0 mmol/L] or severe) during treatment phase up to Week 26
 
The event rate of participant-reported clinically significant nocturnal hypoglycemia (<54 mg/dL [3.0 mmol/L] or severe) during treatment phase up to Week 26
 

Other Secondary	
To investigate the effect of LY3209590 compared with insulin glargine in additional parameters of diabetes management.	
 
Change in fasting glucose measured by SMBG from baseline to Week 26
 
Time in glucose range between 70 and 180 mg/dL (3.9 and 10.0 mmol/L), inclusive measured during the CGM session that occurs between Week 22 and Week 26
 
Time in hypoglycemia range with glucose <54 mg/dL (3.0 mmol/L), measured by CGM that occurs between Week 22 and Week 26
 
Time in hyperglycemia range with glucose >180 mg/dL (10.0 mmol/L), measured by CGM that occurs between Week 22 and Week 26
 
Glucose variability measured during the CGM session that occurs between Week 22 and Week 26
 
Insulin dose at Week 26 
 
basal
 
bolus
 
total, and
 
basal/total insulin dose ratio
 
 
 

To investigate the safety of LY3209590 compared with insulin glargine.	
 
Incidence and rate of composite of Level 2 and 3 hypoglycemia events during treatment period
 
Body weight change from baseline to Week 26
 

To investigate the treatment impact of LY3209590 compared with insulin glargine on patient-reported outcome measures.	
 
Treatment experience at Weeks 26 for DID-EQ
 

Tertiary	

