Analysis Model	
After the imputation, the observed and imputed data will be analyzed by the ANCOVA model using treatment, strata (country, routine use of personal CGM or FGM at randomization), and baseline value of the dependent variable as independent variables. The statistical inference will be based on the multiple imputation framework by Rubin (1987).
	
The MMRM model will include treatment, strata (country, and routine use of personal CGM or FGM at randomization), visit and treatment-by-visit interaction as fixed effects, and baseline value of the dependent variable as a covariate. The Kenward-Roger approximation will be used to estimate denominator degrees of freedom for the MMRM models. An unstructured covariance structure will be used to model the within-participant errors. If this structure fails to converge, the following covariance structures will be used in order until one converges:
 
 
1. Toeplitz with heterogeneity
 
2. Autoregressive with heterogeneity
 
3. compound symmetry with heterogeneous variances
 
4. Toeplitz
 
5. Autoregressive
 
6. Compound symmetry without heterogeneous variances.
 

Abbreviations: ANCOVA = analysis of covariance; CGM = continuous glucose monitoring; EAS1 = efficacy analysis set 1; EAS2 = efficacy analysis set 2; FGM = flash glucose monitoring; HbA1c = hemoglobin A1c; MMRM = mixed model repeated measurement.

The 2-sided 95% CI of the LS mean difference (LY3209590 – insulin glargine) in the HbA1c (in %) change from baseline at Week 26 (Visit 23) will be estimated. For both estimands, LY3209590 will be declared noninferior to insulin glargine if the upper limit of the 2-side 95% CI for the LS mean difference in the HbA1c change from baseline is below NIM of +0.4%. In addition, the 95% CI for the LS mean difference will be compared to an alternative NIM of +0.3%.

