## 4.6. Safety Analyses

Safety measures include treatment exposure, adverse event (AE), vital signs, weight, hypoglycemia, laboratory measures and immunogenicity. All safety analyses will be based on the SS. Unless otherwise specified, safety analysis period will include both treatment period and follow-up period as specified in Section 4.1. Percentages will be calculated using the safety population as the denominator. For events that are gender-specific, the denominator and computation of the percentage will include only participants from the given sex. Unless otherwise noted, Fisher's exact test will be used for treatment comparison, risk difference and 95% confidence intervals will be provided.

For continuous safety variables (for example, laboratory measures, vital signs, and weight), descriptive statistics for the observed values and change from baseline at scheduled visits during the treatment period and follow-up period will be provided. For some selected laboratory measures (i.e. liver enzyme tests, lipid measures), observed values, change from baseline and percentage change from baseline will be analyzed for the log-transformed values by the MMRM model using treatment, visit, and treatment by visit as fixed effects, baseline of the dependent variable as a covariate, and compound symmetry as the variance-covariance structure.

The incidence and event rate of participant-reported and CGM-based hypoglycemia will be summarized by treatment and analysis period for different types of hypoglycemia. Analysis details are provided in Section 0.

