#### 4.6.2.5. Vital Signs and Physical Characteristics

The planned summaries are provided in the Table below. The measurements analyzed for vital signs and physical characteristics include systolic BP, diastolic BP, pulse, weight, and BMI.

Analysis Type	Analysis Details
Observed values change by visit	
 
Includes all participants in the safety population who have both a baseline and at least 1 postbaseline observation
 
MMRM model (as described in Section 4.6) will be used.
 
 
See also: Table 6.2 from the Analyses and Displays for Labs white paper (PHUSE 2022)

Summary by category	
 
Definitions provided in Tables 31-33 from FDA's September 2022 Standard Safety Tables and Figures document will be used for the numerator. 
 
Systolic BP (mm Hg): 
 
Low: Level 1: <90
 
High: Level 1: <math>\geq 90</math>, Level 2: <math>\geq 120</math>, Level 3: <math>\geq 140</math>, Level 4: <math>\geq 160</math>, Level 5: <math>\geq 180</math>
 
 
 
Diastolic BP (mm Hg): 
 
Low: Level 1: <60
 
High: Level 1: <math>\geq 60</math>, Level 2: <math>\geq 90</math>, Level 3: <math>\geq 110</math>, Level 4: <math>\geq 120</math>
 
 
 
 
 
Includes participants with at least one postbaseline measurement.
 
Statistical comparisons (using methods described in Section 4.6) will be included.
 

Participants meeting CTC grade changes in weight	
For weight, cutoffs informed by CTCAE version 5 (Grades 1-3) will be used:
 
 
(Loss) decrease: Level 1: <math>\geq 5\%</math>, Level 2: <math>\geq 10\%</math>, Level 3: <math>\geq 20\%</math>
 
(Gain) increase: Level 1: <math>\geq 5\%</math>, Level 2: <math>\geq 10\%</math>, Level 3: <math>\geq 20\%</math>
 
 
Includes participants with both a baseline and at least 1 postbaseline observation.
 
 
Statistical comparisons (using methods described in Section 4.6) will be included.
 

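### Body weight at Week 26 reaches its model only by cross-reference; the model's compound symmetry understates the Week 26 standard error if weight variance rises over time

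*SAP*

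**What the plan says.** SAP 1.1 lists "Body weight change from baseline to Week 26" among the other secondary endpoints. SAP 4.4.2.2 sends safety endpoints that are not CGM-based to Section 4.6. Within that section, 4.6.2.5 says: "The measurements analyzed for vital signs and physical characteristics include systolic BP, diastolic BP, pulse, weight, and BMI". For observed values and change by visit it adds: "MMRM model (as described in Section 4.6) will be used".

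Section 4.6 describes only one such model, an "MMRM model using treatment, visit, and treatment by visit as fixed effects", with "baseline of the dependent variable as a covariate, and compound symmetry as the variance-covariance structure". The sentence holding that description opens: "For some selected laboratory measures (i.e. liver enzyme tests, lipid measures), observed values, change from baseline and percentage change from baseline will be analyzed". It concerns log-transformed values. For weight, the same paragraph of Section 4.6 promises only descriptive statistics.

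The observation table in SAP 4.1 takes weight from all scheduled visits after first dose up to Visit 802, for MMRM or ANCOVA. Protocol 9.3.5 also allows either model for continuous safety variables. Neither says which applies to weight.

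For the primary HbA1c MMRM, by contrast, SAP 4.3.2 says: "An unstructured covariance structure will be used to model the within-participant errors". It gives six fallback structures and includes country and routine CGM/FGM use.

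**The concern.** Two features of the inherited model deserve separate treatment.

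**Covariance.** Compound symmetry gives every visit the same variance. Change from baseline is zero by definition at the start, and the spread between participants plausibly widens over the following weeks. If so, the model averages small early variances into the Week 26 standard error, and the interval and p-value for weight are too optimistic. No heterogeneous-variance option, fallback or robust standard error is stated.

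**Strata.** Randomization is stratified by country, screening HbA1c stratum and routine CGM/FGM use. The weight model contains none of these, although several other models do: the CGM and SMBG glucose models (SAP 4.4.2.1), DID-EQ (4.4.2.3.1) and the CGM hypoglycemia-duration model (4.6.2.2.2).

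At stake is the reported interval and p-value for one listed secondary endpoint, and whether its model is clearly prespecified at all.

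**Working it through.** **No plan figure to reproduce.** The documents give no SD, power or interval width for weight. The variance patterns, the share of variance explained by the strata and the within-participant correlation are assumptions. Sample size and dropout come from SAP 5: 670 randomized 1:1, so 335 per arm, with 15% dropout. 335 × 0.85 = 284.75, consistent with the stated 284 completers per arm.

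**Formula for compound symmetry.** With complete data and a treatment effect at each visit, the model uses the average visit variance for the Week 26 difference. Hence:

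model SE / true SE = √(mean visit variance / Week 26 variance)

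type I error = 2 × (1 − Φ(1.96 × ratio))

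**Illustration.** The Protocol 1.3 week row has 22 visits after first dose: Weeks 1 to 12, 14, 16, 18, 20, 22, 24, 25, 26, 29 and 31. Measurement error is ignored, so the absolute SD cancels.

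- Constant variance: ratio 1.00, type I error 5%.
- Variance proportional to time up to Week 12, then flat: the values sum to 78 + 10 × 12 = 198. The mean is 198/22 = 9.0, and the ratio is √(9.0/12) = 0.87. Type I error is 9%.
- Variance proportional to time throughout: the weeks sum to 78 + 165 + 60 = 303. The mean is 303/22 = 13.77, and the ratio is √(13.77/26) = 0.73. Type I error is 15%.
- Variance proportional to time squared: the squares sum to 650 + 3,537 + 1,802 = 5,989. The mean is 5,989/22 = 272.2, and the ratio is √(272.2/676) = 0.63. Type I error is 21%.

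Other patterns were also tried. An SD growing 1.5-fold from Week 1 to Week 26 gives 0.85 to 0.86. An SD that doubles by Week 12 and then stays flat gives 0.88. An SD that falls by about 10% gives about 1.05, an interval that is too wide. Many visits are by telehealth, so fewer weights may be taken. A 12-visit subset changes little: 0.76 instead of 0.73 for variance proportional to time.

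Across variations in pattern, visit set and measurement error, the ratio is about 0.85 to 0.92 for a Week 12 plateau and 0.62 to 0.77 for linear or quadratic growth. At the two extremes:

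- 0.92: 2 × (1 − Φ(1.80)) = 7%
- 0.62: 2 × (1 − Φ(1.22)) = 22%

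**Formula for the strata.** If the strata explain a share R² of the variance, leaving out balanced stratification factors multiplies the ratio by 1/√(1 − R²). This is 1.01 at R² = 2%, 1.03 at 5% and 1.05 at 10%. Every value is above 1, so the interval is too wide.

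**Simulation.** 600 trials per setting, 335 per arm, 15% dropout completely at random, serial correlation decaying with time, 12 visits including Weeks 29 and 31, and compound symmetry fitted.

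| Variance pattern | Strata R² | SE ratio | 95% CI coverage |
|---|---|---|---|
| Constant | 0 | 1.02 | 95.5% |
| Constant | 10% | 1.09 | 97.5% |
| SD grows 1.5-fold | 0 | 0.83 | 90.0% |
| SD grows 1.5-fold | 10% | 0.94 | 94.2% |
| Proportional to time | 0 | 0.71 | 84.2% |
| Proportional to time | 10% | 0.78 | 86.2% |

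The simulation agrees with the formulas within its noise. With 600 trials, the standard error of a coverage estimate is about 1 to 1.5 percentage points.

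**The case against.** The strongest reply is that the documents do not show the variance of weight change rising at all. A plateau is arguable: weekly titration ends at Week 12, and the design relies on a stable dose about 12 weeks before the endpoint. That objection stands as a limit on size. Under a plateau the loss is modest, and under constant variance there is none.

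Second, the compound-symmetry sentence is about laboratory tests, and ANCOVA remains open for weight. This is true, but it does not rescue the plan. Section 4.6.2.5 names weight and points to the only MMRM that Section 4.6 describes. Read literally, the pointer would even import the log scale. A listed secondary endpoint should not depend on how a reader resolves this.

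Third, compound symmetry and the absence of strata are not peculiar to weight. SAP 4.4.2.1 fixes compound symmetry for SMBG fasting glucose and insulin dose, and the participant-reported hypoglycemia models in 4.6.2.2.1 carry no strata. So the strata argument rests on precision and on consistency with the models listed above, not on a rule that the SAP follows everywhere.

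A reader might also infer that the missing strata and compound symmetry together make the interval too narrow. They do not: the two act in opposite directions, and in one simulated setting they nearly cancel (94.2% coverage). Such a cancellation would be accidental and is no reason to keep either feature.

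**Conclusion.** The point holds in conditional form. By cross-reference, Week 26 weight falls under a compound-symmetry model without strata that was written for other variables. If the variance of weight change rises over time, the Week 26 standard error is understated, with type I error of about 7% to 22% under the growing-variance patterns above. All of those patterns are assumptions. It would be tempting to say that the weight interval is anti-conservative as a fact, but the documents contain no weight variances that would support this.

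Omitting the stratification factors is a smaller, separate matter. It gives up reported precision and makes the standard error about 1% to 5% too large if the strata explain 2% to 10% of the variance.

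The consequence is limited. Weight lies outside the multiplicity-controlled family, and the by-visit descriptive statistics and weight-change categories do not use this model. Primary and key secondary conclusions do not change.

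**What to change.** State the weight model explicitly in SAP 4.6.2.5, on the untransformed scale:

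- Add country, HbA1c stratum and routine CGM/FGM use as fixed effects, as in SAP 4.4.2.1 and 4.6.2.2.2. The primary MMRM cannot simply be copied, because it does not contain the HbA1c stratum. Say whether the screening or the baseline stratum is meant, since randomization used the screening value.
- Use an unstructured covariance with the Section 4.3.2 fallback order. Its first three fallbacks still let the variance differ by visit.
- Alternatively, specify a Week 26 ANCOVA with the same factors and baseline weight. SAP 4.1 and Protocol 9.3.5 already permit ANCOVA.

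The cost is SAP wording, to be settled before unblinding. The drawback is size: with 22 visits an unstructured matrix has 22 × 23 / 2 = 253 parameters, so the model may need fewer visits or a fallback structure. The ANCOVA avoids this but uses no intermediate weights unless missing Week 26 values are handled separately.

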### 4.6.1. Extent of Exposure

Duration of exposure to study treatment will be summarized. No p-values will be reported in these tables as they are intended to describe the study populations, rather than test hypotheses about them. Total patient-years of exposure will be reported. The number and proportion of participants falling into the following different exposure categories will also be summarized by study treatment

- $>0, \geq 30$  days,  $\geq 90$  days,  $\geq 180$  days
- $>0$  and  $< 30$  days,  $\geq 30$  and  $< 90$  days,  $\geq 90$  and  $< 180$  days,  $\geq 180$  days

Exposure on study treatment will be calculated as

- LY3209590: date of the last treatment administration – date of first treatment administration + 7 days
- Insulin glargine: date of the last treatment administration – date of first treatment administration + 1 day

Total patient-years of exposure will be calculated by the sum of duration of exposure in days divided by 365.25. The following summary statistics will be provided: n, mean, standard deviation, median, minimum, maximum, interquartile range, and total exposure (that is, total patient-years).

All participants who complete the study treatment period are required to complete a safety follow-up period and participants who discontinue the study treatment prematurely are encouraged to remain in the study for safety monitoring. The duration on study from the first dose of study treatment to the study disposition date will also be summarized by treatment.

A listing of exposure to study treatment will be provided.

#### 4.6.2. Adverse Events

Events that are newly reported after the first dose of investigational product (IP) or reported to worsen in severity from baseline will be considered treatment emergent adverse events (TEAEs). The Medical Dictionary for Regulatory Activities (MedDRA) lowest level term (LLT) will be used in the treatment-emergent assessment. The maximum severity for each LLT during the baseline period (see the table in Section 4.1) will be used as baseline severity.

The table below describes the analysis related to AEs.

Analysis	Details
Overview of AEs	
Number and percentage of participants who experienced:
 
 
• SAE
 
• Death
 
• Discontinuation from study treatment due to an AE
 
• Discontinuation from study due to an AE
 
• TEAE
 
• TEAE related to study treatment
 

Summary by PT within SOC	
Number and percentage of participants with AEs using MedDRA PT nested within SOC:
 
 
• TEAE
 
• Maximum Severity TEAEs
 
• SAE
 
• AE leading to permanent discontinuation of study treatment
 
 
Events will be ordered by decreasing risk difference within SOC. SOCs will be listed by decreasing risk difference.
 
For each participant and TEAE, the maximum severity for the MedDRA PT is the maximum postbaseline severity observed from all associated LLTs mapping to the MedDRA PT. The maximum severity will be determined based on the non-missing severities.

Summary by PT (within SMQ when applicable)	
Number and percentage of participants with TEAEs using MedDRA PT (irrespective of SOC):

Analysis	Details
	
 
TEAEs occurring in <math>\geq 1\%</math> before rounding in LY3209590 group. Events will be ordered by decreasing risk difference and by decreasing frequency in LY3209590 group, respectively
 
TEAE of safety topic of interest by PT (within SMQ when applicable). Events will be ordered by decreasing risk difference.
 

Listing	
Separate listings for the following events will be provided:
 
 
SAE including death
 
AEs leading to study treatment discontinuation
 
Severe hypoglycemia
 
Events sent to the external adjudicator for MACE adjudication
 
Participants who receive rescue therapy due to severe/persistent hyperglycemia
 
Persistent-recurrent hypoglycemia reported by investigators
 
Persistent-recurrent hypoglycemia identified by programming
 
Medication errors of interest
 

Abbreviations: AE = adverse event; LLT = lowest level term; MACE = major adverse cardiovascular event; MedDRA = Medical Dictionary for Regulatory Activities; SAE = serious adverse event; SOC = System Organ Class; PT = preferred term; TEAE = treatment emergent adverse event.

#### 4.6.2.1. Safety Topics of Interest

##### 4.6.2.1.1. *Severe Hypoglycemia*

Severe hypoglycemia is a severe event characterized by altered mental and/or physical status requiring assistance for treatment of hypoglycemia. The determination of a hypoglycemic event as an episode of severe hypoglycemia is made by the investigator based on the medical need of the participant to have required assistance and is not predicated on the report of a participant simply having received assistance. If a hypoglycemic event meets the criteria of severe hypoglycemia, the investigator must record the event as serious on the AE case report form (CRF).

A summary of severe hypoglycemia by preferred term (PT) and ordered by decreasing risk difference between LY3209590 and glargin will be provided. Section [4.6.2.2.1](#) describes the method for analyzing the incidence and event rate during the treatment period. A listing of severe hypoglycemia events will also be provided.

##### 4.6.2.1.2. *Persistent-Recurrent Hypoglycemia*

The potential risk of persistent-recurrent hypoglycemia (P-R hypoglycemia) will be assessed from the first dose date up to the end of the study. P-R hypoglycemia events will be identified using

1. investigator assessment and clinical judgment to determine if repeated hypoglycemia may have contributed to a hypoglycemic event that degenerated with poor outcomes, and
2. a prespecified criteria to derive events from e-diary database by programming (see definition Appendix 9, Figure BDCV. 6.9.).

Identification of P-R hypoglycemia based on investigator reporting is precipitated by a hypoglycemic event a participant or their caregiver informed as having resulted in a poor

outcome. This information will trigger an e-mail alert notifying the investigator to contact the study participant, obtain more information about the specific hypoglycemic event, and provide the participant clinical guidance, if appropriate. Hypoglycemic events that trigger alerts to investigators are those participants or caregivers report in the e-diary have required treatment with glucagon or IV glucose, resulted in coma, motor vehicle accident or other trauma, hospitalization, or emergency medical care.

Upon receiving the e-mail notification, investigator will access the e-diary database and answer the following question: *"In your clinical judgement, is this hypoglycemia event associated with repeated hypoglycemia events?"*. Investigator should select "Yes" or "No" as an answer.

During protocol training, investigators are trained to consult the e-diary database and review participant's BG values and hypoglycemia reports to determine the best answer. If the investigator judges the hypoglycemic event that triggered an alert is related to repeated episodes of hypoglycemia, the participant will be identified as having presented a P-R hypoglycemic event reported by the investigator.

Summary statistics and a listing of the events identified by both methods will be provided.

